SynePure Wound Cleanser and Catasyn Advanced Technology Hydrogel demonstrates an improvement in healing, scarring, fibrosis, and infection of burn wounds and complex open wounds. Its toxicity profile, ability to remove biofilms, healing, and anti-inflammatory properties make a compelling case for further testing of SynePure Wound Cleanser and Catasyn Advanced Technology Hydrogel as a new agent to facilitate healing and limit scarring in burn wounds.

3.0 Research Design and Methods:

The study is a prospective, parallel group, randomized controlled trial comparing SynePure Wound Cleanser and Catasyn Advanced Technology Hydrogel (intervention group) to the current gold standard treatment Silvadene (control group). Subjects will be randomized 1:1, either to the treatment group or the standard of care (Silvadene) control group.

Prior to the candidate's referral into the study, as part of standard of care in the burn center, the burn wound is debrided and cleansed in the hydrotherapy area, and then assessed to categorize the burn (superficial, partial thickness,).

Procedural Summary:

- 1. After informed consent process is completed, the study investigator examines and screens the participant to confirm the diagnosis of a superficial-partial thickness burn and all other eligibility inclusion/exclusion criteria. Medical history, medical record review with participant report, medication profile collections, vital signs, demographics, physical exam with burn wound and surface area assessments are completed at this time. Upon completion of these assessments' all findings are reviewed and participant eligibility is determined based on study inclusion and exclusion criteria.
- 2. Should participant be deemed eligible to continue in research; randomization is performed to determine group assignment with randomization to either the intervention group (SynePure Wound Cleanser and Catasyn Advanced Technology Hydrogel) or the control group (Silvadene). Prior to application of treatment agent and dressing application, 2D photographs will be taken of the burn area for later evaluation.
- 3. During the Initial treatment visit (Day 0), after randomization, the treatment agent is applied (SynePure Wound Cleanser and Catasyn Advanced Technology Hydrogel or Silvadene) to complete secondary dressing with a dry gauze and Kerlix wrap application.

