- 4. Patient education on wound care and daily dressing change per routine care. Dressing to be changed daily by patient or provider. Education also provided as to the treatment agent to be applied daily with the dressing change (SynePure Wound Cleanser and Catasyn Advanced Technology Hydrogel or Silvadene).
- 5. Participants will be asked to complete Subject report questionnaires related to the burn wound, symptoms experienced and effects of injury on their activities of daily living.
- 6. The research coordinator will call the participant twice at timepoint Day 1 and Day 3 to assess participant safety, complications/adverse events and address any questions or concerns that the participant may have encountered.
- 7. Follow-up Visits (Visits 2-8) will occur in the UPMC Mercy Burn Center and will consist of wound evaluation, brief history and physical assessment, vital signs, recording of status change since last visit/interaction, medication review, and adverse event collection. 2D photographs will be obtained of burn wound area at time of physical assessment and Subject report questionnaires and wound dressing assessment /treatment agent application (if wound has not yet healed). Reference to the Schedule of Events included with Protocol for additional detail of study procedures.

Recruitment:

Subjects presenting to the study site for treatment of superficial partial thickness burns will be considered for enrollment. Physicians and licensed clinicians within the burn center area, familiar with the study's inclusion/exclusion criteria will assess for potential patients as they arrive to the

Burn Center Clinic for treatment, a part of their burn practice. If the patient is an appropriate candidate and willing to be considered for the study, he/she will be referred to the research team.

After informed consent has been obtained, the study investigators will conduct screening procedures to determine study eligibility. Should the participant meet criteria, he/she will proceed to randomization on Day 0 prior to treatment application. Enrolled subjects will be randomly assigned per a predefined 1:1 randomization scheme to either the interventional group or control group.

Active Treatment:

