During the initial treatment visit (Day 0), the wound will undergo hydrotherapy debridement per routine care and at which time 2D photographs of the wounds will be obtained prior to randomization. Participants assigned to each group will have their treatment applied per their randomization status, either SynePure Wound Cleanser and Catasyn Advanced Technology Hydrogel (intervention group) or Silvadene (control group). They also will be given written instructions on how to apply the treatment at home and a sufficient supply to last until their next visit.

Consent and Screening procedures:

All screening procedures will be performed at the UPMC Mercy burn center in a private room after this informed consent document is signed. These screening procedures will take approximately 2-3 hours.

- Informed consent
- Review of medical records related to the injury, past surgeries, and general health events
- Demographic information and allergy collection
- Physical assessment inclusive of an evaluation to your burn wound area
- Medication collection
- Vital sign measurement (such as temperature, heart rate, blood pressure and respiration rate) collection
- Pregnancy Test (Urine Dip)

Initial Treatment Visit 1 (Day 0):

After all screening procedures have been completed and reviewed by the investigators and eligibility will be determined. Should the participant be determined to be eligible to continue participation, the initial treatment procedures will be continued and all procedures may occur on the same day as the screening visit. This visit will be performed at the UPMC Mercy Burn Center. The total length of time for this visit will take approximately 2-3 hours of time.

- Randomization process with assignment to 1 of 2 treatment groups where either SynePure Wound Cleanser with Catasyn Advanced Technology Wound Hydrogel OR Silvadene will be applied. Both groups will then receive a secondary dry dressing covering consisting of gauze and Kerlix wrap.
- 2D photographs will be obtained focusing on the burn injury area, prior to the wound being dressed.
- Written instructions will be provided describing how to apply the wound treatment and
 dressings daily in between to the participant. Should the participant be in hospital
 during the healing of the burn wound these daily dressings will be performed by either a
 member of the clinical staff or the research team.

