- Completion of Subject Self-report questionnaires that pertain to the burn wound, pain, and other symptoms that experience. Potential effects and relationship to the participant's quality of life and activities of daily living
- Adverse events collection

After this initial visit, the research team will reach out to the participant by phone on Day 1 and Day 3 of the study schema to determine if there are any questions, issues or concerns that the participant may be experiencing. Additionally, they will remind and confirm the next in person visit to the clinic.

Follow-up Visits (Visits 2-8):

These Visits will occur in the UPMC Mercy Burn Center and have a duration of 1-2 hours to complete. These visits will consist of wound evaluation to assess for healing, brief history and physical assessment, vital signs, recording of status change since last visit/interaction, medication review, and adverse event collection. 2D photographs will be obtained of burn wound area at time of physical assessment and prior to wound dressing /treatment agent application (if wound has not yet healed) and subject report questionnaires consisting of SF-12, Wound Experience and Satisfaction questionnaires, Vancouver Scar Scale, POSAS Questionnaires (described in the following section). During the study visit, continued instructions for at home dressing and treatment application will be reinforced.

Subject Reported Questionnaires:

Vancouver Scar Scale Score: The VSS⁹ is a scale to assess the extent of scarring for a given wound by scoring the pigmentation, vascularity, pliability and height of the scar. Each domain is individually scored then the domains are summed to give a total score that range from zero (0) to 13 with zero (0) representing a 'normal' presentation. Validity and reliability of the scale have been documented 10-12 and is commonly used in wound healing research.

SF-12: The SF-12¹³, an abbreviated version of the SF-36, is a patient self-reported twelve questions survey of general health, physical functioning, role functioning (physical and emotional), bodily pain, vitality, mental health, and social functioning. The scale is comprised of two scores: physical component summary (PCS) and mental component summary (MCS). Scores are summarized and normalized. While the survey demonstrates moderate validity and reliability, ¹⁴ the survey is ideal for use as it is brief and commonly used, so comparisons between studies are possible.

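### As listed, the Day 0 questionnaires follow randomization and first application, so general-health, pain and symptom items have no stated pre-randomization value

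*Combined protocol and SAP*

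**What the plan says.** The protocol describes Day 0 in three places within section 3.0.

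- **Procedural Summary.** At step 2, "randomization is performed to determine group assignment with randomization to either the intervention group" or the control group. Step 3: "During the Initial treatment visit (Day 0), after randomization, the treatment agent is applied". Step 4: "Education also provided as to the treatment agent to be applied daily with the dressing change". Step 5: "Participants will be asked to complete Subject report questionnaires related to the burn wound, symptoms experienced". Step 6 is the Day 1 and Day 3 telephone calls.
- **Initial Treatment Visit 1 (Day 0).** The list begins with randomization and dressing, then photographs, then written home instructions, and only then "Completion of Subject Self-report questionnaires that pertain to the burn wound, pain, and other symptoms".
- **Consent and Screening procedures.** Seven items, none of them a questionnaire.

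No instrument is named for Day 0. The SF-12, the wound experience and satisfaction questionnaires, the VSS and the POSAS are named for Visits 2 to 8.

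The Analytic Plan (section 3.1) analyses patient-reported outcomes by repeated-measures ANOVA, with days since wounding as the within-subject factor and treatment as the between-subject factor. It names no baseline covariate and does not say whether Day 0 is one of the levels.

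On the baseline photograph, the Active Treatment paragraph says "at which time 2D photographs of the wounds will be obtained prior to randomization". Step 2 of the Procedural Summary says "Prior to application of treatment agent and dressing application, 2D photographs will be taken of the burn area for later evaluation", and the Visit 1 list ties the photograph only to the dressing.

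**The concern.** Patient-reported outcomes are Specific Aim 3, and the Day 0 questionnaires cover pain and other symptoms. No masking is described. Because step 4 teaches participants which agent they will apply at home, it is reasonable to infer that they know their arm by step 5.

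Section 4.5 lists a burning sensation among the risks of Silvadene and only a low risk of redness for the hydrogel. It gives no timing for either, but an early difference in symptom answers is plausible, and so is a reaction to learning the allocation. A Day 0 score collected at that point may already hold part of the treatment effect. Any analysis that treats it as a starting value would then subtract or distort that part, and the arms' comparability on these items before treatment could not be described.

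**Working it through.** The protocol gives no sample size, SD or correlation for any patient-reported outcome, so there is no figure of its own to reproduce. Every value of δ, d, r and ρ below is an assumption. The 45 per arm comes from the Sample Size Estimation, which was made for time to healing.

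**1. Order of procedures.** The numbered summary runs randomize, apply, teach, questionnaires, telephone calls. Step 3 states its own timing relative to randomization; step 5 carries no timing words. The Visit 1 list agrees on the order but is not strictly chronological, since its photograph item follows the dressing item and yet is to be done before dressing. No place in the text reviewed puts a questionnaire before randomization.

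**2. Which contrasts are exposed.** Let δ be the arm difference at each follow-up visit and d the arm difference already present at Day 0, both in SD units and in the same direction.

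- Arms compared at a follow-up visit: δ. The Day 0 value does not enter.
- Group-by-day contrast, or change from Day 0: δ − d. With d of 0.1 to 0.3, the shift is 0.1 to 0.3 SD. For δ = 0.5 the contrast becomes 0.4 to 0.2.
- Follow-up adjusted for Day 0 with slope r: δ − r·d. For r of 0.3 to 0.7, the shift runs from 0.3 × 0.1 = 0.03 to 0.7 × 0.3 = 0.21 SD.

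**3. Effect of moving the questionnaires but leaving the ANOVA as it is.** Before randomization d = 0 in expectation. If Day 0 is kept as one of eight visits (Visit 1 plus Visits 2 to 8), the group main effect becomes (7δ + 0)/8. For δ = 0.5 that is 0.4375.

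Under compound symmetry with correlation ρ, the variances are (1 + 7ρ)/8 for the mean of eight visits, (1 + 6ρ)/7 for the mean of seven, and (1 + 6ρ)/7 − ρ² for the mean of seven adjusted for baseline. Power is Φ(effect / (SD × √(2/45)) − 1.96), two-sided 0.05.

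| ρ | Day 0 as an outcome level | Seven follow-up visits only | Seven visits, Day 0 as covariate |
|---|---|---|---|
| 0.3 | 91.5% | 96.3% | 98.9% |
| 0.5 | 79.0% | 88.1% | 98.7% |
| 0.7 | 67.6% | 78.6% | 99.7% |

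For ρ = 0.5 in the first column: SD = √0.5625 = 0.75, and 0.4375 / (0.75 × 0.2108) = 2.77, which gives 79%. Moving the questionnaires without changing the analysis would dilute the main effect.

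**4. Precision at a single visit.** With 45 per arm and 80% power, the detectable difference without a baseline is (1.960 + 0.842) × √(2/45) = 0.59 SD. Adjustment multiplies it by √(1 − ρ²), giving 0.56, 0.51 and 0.42 SD for ρ of 0.3, 0.5 and 0.7. A post-application Day 0 score could also reduce variance, but only a pre-randomization score does so without the r·d shift.

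**5. Cost in questionnaires.** Section 4.1 plans 115 consented and 100 randomized. Collection at screening adds up to 115 − 100 = 15 sets. Collection after eligibility is confirmed adds none.

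**The case against.** The strongest reply is that no sentence says the questionnaires follow application. The order is read from list position, one of the two lists is demonstrably not chronological, and the Schedule of Events to which the protocol refers was not in the text reviewed and may settle the timing. This stands as a limit on certainty. It does not remove the point, because a numbered sequence is what site staff would follow, and the narrative would need aligning even if the Schedule gives a different order.

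A second reply is that the d and r·d shifts belong mainly to change-score and adjusted analyses, and the Analytic Plan names neither. That is correct. A reader might infer that the planned between-arm comparisons of patient-reported outcomes are biased; the documents do not support this. Only the group-by-day interaction is exposed as planned, and only if Day 0 is a level.

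Three other readings go too far.

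- *Every patient-reported outcome lacks a baseline it could have had.* The VSS and POSAS rate a scar that has not yet formed, and satisfaction with the assigned dressing cannot be asked before it is worn.
- *Moving the questionnaires is free.* Step 3 of the working shows that the analysis text must change as well, and collection at screening adds questionnaire sets.
- *The photograph passages contradict each other.* A photograph taken before randomization is also taken before application and before dressing, so all three statements can be met. Step 1 of the Procedural Summary also completes the wound and surface-area assessment before randomization.

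**Conclusion.** The point holds for general-health, pain and symptom items, on the order as listed. No pre-randomization value is described for them, and the participant appears to know the arm and to have been treated when first asked. The consequence is limited: the group-by-day interaction and any use of Day 0 as a starting value are exposed, while between-arm comparisons at follow-up visits are not.

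The size cannot be found from the documents; the ranges in the working illustrate the mechanism and do not estimate it. The gain from the change depends on the Day 0 score being used as a covariate and on its correlation with later scores. Patient-reported outcomes serve Aim 3 and not the healing endpoint, so this is a worthwhile, inexpensive improvement and not a threat to the primary result. Nor would it remove any effect of knowing the allocation on follow-up answers.

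**What to change.** 1. In the Procedural Summary, the Visit 1 list and the Schedule of Events, state that the general-health (for example SF-12) and pain/symptom items are completed on Day 0 after eligibility is confirmed and before randomization. Name the instruments, since none is named for Day 0.
2. Leave the VSS, the POSAS and the dressing-satisfaction items at post-treatment visits. If the pain or symptom items come from the Wound Experience Questionnaire, say which sections are used when. Splitting it alters an instrument for which the protocol already reports no published validity evidence.
3. In the Analytic Plan, state that the repeated-measures analysis covers the follow-up visits, with the Day 0 score as a baseline covariate and not as an outcome level.
4. Word the photograph timing in step 2 and in the Visit 1 list as in the Active Treatment paragraph, before randomization. This is a clarification.

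The cost is a small change in Day 0 workflow and a few lines of protocol and analysis text. Screening and Visit 1 may already share a day, so no visit is added, and no further patient has to be randomized. There are no extra questionnaire sets if collection follows eligibility, and up to about 15 if it is done at screening.

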POSAS: The patient and observer scar assessment scale¹⁵⁻¹⁶ is used to measure scar quality. It is composed of a patient reported section and an observer reported section. Each section consists of six items that are scored numerically on a ten-step scale. These are then summed together to make up the total score. There is also an overall opinion section for both the patient and the observer. While validity and reliability are marginal for the POSAS, scores have shown little variance from the gold standard, the Vancouver Scar Scale, and it has the distinct advantage of incorporating the patient's perspective.

Wound Experience Questionnaire: The wound experience questionnaire ¹⁷ consists of three sections regarding the patient's wound. The questionnaire is used for wounds early into the healing process and wounds that have dressings. This has been primary used in patients with surgical wounds but can be adapted to wounds not specifically operative, such as burns. Validity and reliability evidence have not been published but the questionnaire has the unique capability to assess a primary focus of this study. In addition to assessing patient satisfaction with the healing process, the questionnaire also assesses patient satisfaction with the wound dressings as distinct categories.

3.1 Data Collection and Statistical Consideration:

Sample Size Estimation:

In this study, the minimal median difference of three (3) days to healing is determined to be the clinically relevant difference. Given an assumed median time of 15 days to healing for the Silvadene comparator group 18 , a corresponding hazard ratio of 0.8 for the intervention group is anticipated. a sample of 45 in each group (90 total) is required to detect a statistically significant difference [confidence level ($\alpha \leq 0.05) - 95\%$; Power - 80%]. Assuming a 10% attrition, it is recommended to enroll up to 100 subjects to achieve a sample of 90 subjects. This will be easily accomplished in our outpatient burn clinic, with a 400-patient annual volume, and we will use a 3-week evaluation period so that the trial can be accomplished in a year.

Analytic Plan:

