Descriptive statistics will be presented as means and standard deviations for continuous data and as counts and percentages for dichotomous and categorical data. Time-to-event curves with Kaplan-Meier (KM) estimates will be used to compare overall median time to wound healing between treatment groups. Comparison of KM curves will be performed using the log rank test as the curve is assumed to be non-parametric or semi-parametric, and the baseline hazard is not related to the group assignment. Relevant clinical and demographic variables may be assessed for their independent contribution in time-to-event outcome using univariate screening and the hazard is assumed to be relatively constant across the study window. Multiple regression modeling (Cox Proportional Modeling) and adjusted KM curves will be assessed as appropriate. Variables will be included in the multivariate analysis if the univariate screening p-value is < 0.10 and multivariate parameters will be presented as hazard ratios with their corresponding 95% confidence intervals.

Infection, complication, and progression rates will be compared using the Chi-squared test or the Fisher exact test if the data is very unequally distributed within the contingency table, which is anticipated for infection rates. Repeated Measure Analysis of Variance (ANOVAs) will be performed to assess differences in PROs with the days since wounding as the Within-Subjects factor and treatment groups as the Between-Subjects factors. Bonferroni post-hoc analyses may be performed for all statistically significant main effects. Baseline demographic and clinical characteristics will be compared between treatment groups with Independent samples t-test for continuous data and Chi-squared test for dichotomous and categorical data.

Analysis will be performed using SPSS (IBM SPSS Statistics for Windows, Version 25.0. Armonk, NY: IBM Corp.) and statistical significance will be determined at $p \le 0.05$ with the exception of univariate screening as previously described.

Outcome definitions:

- 1. Healed wound: 90% reepithelialization (skin and mucous membrane replacement) of the wounded area.
- 2. Infection: characterized by local new inflammation, heat, purulence as well as new or increased pain, redness and swelling
- 3. Complications other than infection: gangrene, necrosis, periwound dermatisis and/or edema, hematoma, or any other complication determined to be related to the wound and/or treatment

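### The stated 80% power does not follow from the plan's own inputs: 45 per group gives about 14–18% power for a hazard ratio of 0.8

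*Combined protocol and SAP*

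**What the plan says.** All of this is in section 3.1 of the combined protocol and SAP.

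- **Target effect** (Sample Size Estimation): "the minimal median difference of three (3) days to healing is determined to be the clinically relevant difference".
- **Control median**: "Given an assumed median time of 15 days to healing for the Silvadene comparator group".
- **Effect measure**: "a corresponding hazard ratio of 0.8 for the intervention group is anticipated".
- **Sample size**: "a sample of 45 in each group (90 total) is required to detect a statistically significant difference", given for alpha 0.05 and 80% power. A 10% attrition allowance takes 90 to 100.
- **Follow-up**: "we will use a 3-week evaluation period so that the trial can be accomplished in a year".
- **Test** (Analytic Plan): "Comparison of KM curves will be performed using the log rank test".
- **Hazard shape** (Analytic Plan, in the sentence on covariate screening): "the hazard is assumed to be relatively constant across the study window".

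The section gives no formula, event count, standard deviation, software or sidedness for the sample size.

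**The concern.** The inputs agree with one another: 12/15 = 0.8 is the exponential conversion of medians of 15 and 12 days into a hazard ratio. The sample size does not agree with them. A log-rank test draws its power from events, and a hazard ratio of 0.8 is a modest effect that needs several hundred. The plan states no event count. It quotes a number of subjects, although a 3-week window need not see every wound heal.

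Time to healing is the only outcome for which the plan gives a sample size. If the hazard ratio really is 0.8, the comparison would miss it about five times in six. A non-significant result could then be read as a negative finding from an 80%-power trial, which this would not be.

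**Working it through.** **Inputs.** From section 3.1: hazard ratio 0.8, medians 15 and 12 days, 45 per group, alpha 0.05, 80% power, log-rank test, 3-week evaluation period. Section 3.0 gives 1:1 allocation. Sidedness is not stated, so two-sided is taken as the default and one-sided is also shown. A ratio of 0.8 and a healing ratio of 1/0.8 = 1.25 have the same absolute log, 0.2231, so direction does not affect the event formula.

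**1. Trying to reproduce the plan's figure.** Events needed for 80% power, two-sided:
- Schoenfeld: 4(1.960 + 0.8416)² / (ln 0.8)² = 630.5, so 631.
- Freedman: (1.960 + 0.8416)² × (1.8/0.2)² = 635.8, so 636.
- One-sided 0.05: 497 and 501.

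None is near 90. The attrition step does reproduce: 90/0.90 = 100.

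**2. Expected events.** The upper limit is 90, if every wound heals under observation. With exponential healing and censoring at day 21, the proportions unhealed are 0.5^(21/15) = 37.9% and 0.5^(21/12) = 29.7%. Events = 45 × 0.621 + 45 × 0.703 = 59.6.

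**3. Power at a hazard ratio of 0.8.** Power = Φ(0.2231 × √d / 2 − z), where d is the number of events and z is 1.960 (two-sided) or 1.645 (one-sided).

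| Events | Two-sided 0.05 | One-sided 0.05 |
|---|---|---|
| 59.6 (90 subjects, day 21) | 13.6% | 21.7% |
| 90 (all heal) | 18.4% | 27.9% |
| 66.2 (100 subjects, no attrition, day 21) | 14.6% | 23.1% |
| 100 (100 subjects, all heal) | 19.9% | 29.8% |

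A log-rank simulation with 20,000 runs, 45 per group and two-sided testing gave 13.8% with day-21 censoring and 18.2% without.

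**4. What the design can detect at 80% power, two-sided.**
- 90 events: exp(2 × 2.8016/√90) = 1.81, a median of 15/1.81 = 8.3 days against 15.
- Day-21 censoring: the event count depends on the effect, so the two are solved together. At a ratio of 1.99 the intervention median is 7.5 days, events are 45 × (2 − 0.5^1.4 − 0.5^(1.4 × 1.99)) = 66.4, and exp(2 × 2.8016/√66.4) = 1.99.

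**5. Where 45 could come from.** A two-sample t-test with standardized difference 0.6 (for example 3 days over an SD of 5) and 45 per group has 80.4% power. This is a numerical match only. No SD appears in the documents, and a t-test is not the planned comparison of healing times.

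**The case against.** The best defence is that the clinically relevant effect is the 3-day difference, and the hazard ratio is only its translation. If healing times are less spread than exponential, the same medians imply a stronger ratio. With a Weibull shape of 2.65 (an assumption), the ratio is (15/12)^2.65 = 1.81. Power is then 80% with 90 events and 75% with the 80 expected by day 21. A shape of 2 gives 56% and 48%. So the trial is not shown to be underpowered for 3 days under every healing pattern. This point stands, but it does not rescue the stated calculation: at 0.8, 90 events give 18% whatever the shape of the hazard. On this reading the hazard ratio is the error, and the paragraph still needs correcting.

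The 14% figure is also open to challenge. The 3-week period appears in a feasibility sentence, not as a censoring rule, and the constant-hazard remark belongs to covariate screening. That is fair, so 14% must carry its conditions. The 18% figure needs neither.

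Finally, to call a null result uninformative is somewhat strong. With an estimated ratio of 1, the 95% interval would be exp(±3.92/√90), or 0.66 to 1.51, with 90 events, and 0.60 to 1.66 with 59.6. That excludes a doubling of the healing rate but not the 1.25 the trial is sized on.

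**Conclusion.** The concern holds. For the stated hazard ratio, test and alpha, 45 per group does not give 80% power under either standard formula, one-sided or two-sided. Events fall short about sevenfold (631/90).

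Two-sided power is 18.4% if all 90 wounds heal under observation, which rests only on the stated hazard ratio and 1:1 allocation. It is 13.6% if healing is exponential and follow-up stops at day 21. Power near 80% for 15 v 12 days requires a steeply rising hazard, which contradicts both the stated ratio and the plan's remark on a roughly constant hazard. The documents do not show how 45 was obtained.

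**What to change.** Rewrite the Sample Size Estimation paragraph and leave enrolment as it is. One of two forms will do.

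1. **Keep the hazard-ratio basis.** State that 90 evaluable subjects give about 18% power (two-sided 0.05) for a healing hazard ratio of 1.25 if all heal under observation. With exponential healing and 21-day follow-up, the figure is about 14%. State that 80% power is reached only for a ratio of about 1.8 or about 2.0 respectively. Write the ratio as 1.25, or say explicitly that 0.8 is the ratio of medians, since a healing hazard ratio below 1 would mean slower healing on the intervention.
2. **Give the real basis.** If 45 per group came from another method or a non-constant hazard, state the method, its SD or shape parameter and their source. Then remove 0.8, or replace it with the ratio those assumptions imply.

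In either form, state sidedness, the expected number of events and the time at which unhealed wounds are censored. It would also help to say that the hazard ratio will be reported with its 95% confidence interval, and that a non-significant result will not be read as evidence against the target effect. That addition can be decided separately from the correction.

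The cost is one paragraph and a much less favourable power statement.
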